performance gaps, such as more targeted outreach efforts to reach specific populations or more intensive approaches to locating clients who missed appointments.

International and Ukrainian institutions have made significant investments to increase data quality and use to improve HIV outcomes for key populations. The Public Health Center of the Ministry of Health of Ukraine (PHC) in collaboration with the Network of PLWH funded by PEPFAR actively promotes the use of a nationwide Medical Information System (MIS) at the clinic level. The MIS contains patient-level information on HIV care appointments kept, medication prescriptions, all diagnosed co-morbidities, and clinical and laboratory test results. It also includes information on new and previously detected HIV cases. The MIS is also used by NGOs that provide social and medical support for PLWH, allowing for tracking treatment and patient pathways across service sectors and institutions. MIS use has been extended to all regions of Ukraine.¹⁶ PHC created a division to provide support MIS users and developed webinars and other materials to train a wide range of service provider cadre to use the system.¹⁶ PHC is currently working to add new features (such as MAT and hepatitis treatment monitoring) and to expand the use of MIS to facilitate patient tracking and analysis of data on cascade and quality of care indicators at the clinic and oblast (regional) levels.¹⁷ The Ukrainian Institute on Public Health Policy (UIPHP—see Study Team, below) evaluated outcomes of national ART optimization (scale-up of dolutegravir-based regimens) using the MIS data (ART OPTI project). PEPFAR, other international donors, and the PHC recognize the role that effective use of data will play in achieving 90-90-90 targets.

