and medications); and *process data* (enrollment in services, HIV care appointments made and kept, referrals, contact attempts).

Study Sites Consistent with PEPFAR priorities, we will partner with large HIV clinics in four high burden regions: Dnipro, Poltava, Odesa and Kyiv City. We will select 4 sites from the list of clinics that will match the following criteria: (a) at least current 150 patients registered with injecting drug use (IDU) mode of transmission; (b) current provision of case management (Steps Toward Health or other interventions, described below); (c) MIS is fully operational and all patients are entered; (d) administration approval for the site and its clinicians to participate.

Acuity Scale Levels

Management Level	Point Range	Health Status/Medical Condition	Frequency
Level 1: Self-Management	25-35	Client is medically stable and is able to manage supportive needs without assistance.	Face to Face at least once every 6 months for reassessment no phone contact indicated
Level 2: Basic Management	36-60	Client is medically stable and is able to manage supportive needs with minimal assistance	Face to Face every 6 months with at least one phone contact every 3 months
Level 3: Moderate Management	61-84	Client is at-risk of becoming medically unstable without assistance and support systems are not adequate to meet client's immediate needs without support	Face to Face a minimum of every 3 months with at least one phone contact monthly
Level 4: Intensive Management	85-100	Client is medically unstable and in need of comprehensive support for medical and supportive needs	Face to Face at least once a month with phone contacts weekly

Specific Aim 1: Adapt a D2C implementation strategy for Ukraine

We will use the Dynamic Adaptation Process (DAP)—phases I (Exploration) and 2 (Preparation)—to guide the adaptation of a D2C strategy for Ukraine.¹³ The DAP considers the multilevel context of service delivery and engages multiple stakeholders, which is appropriate for a complex structural intervention such as a D2C. Project activities for Aim 1 will include baseline in-depth interviews with service providers, clinic directors, PLWH who inject drugs, and other key stakeholders who will be involved in adapting and implementing the D2C strategy; MIS data module and extraction protocol development; and finalizing the D2C strategy.

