- knowledge of and experiences with organizations that assist PLWH and PWID;

D2C Ukraine

- experiences with these agencies, including how they learned about them, motivation for seeking help, eligibility criteria, and application procedures;
- experiences of service denial, perceived or experienced stigma, and treatment by staff;
- ideas about what services are still needed [SEE APPENDIX B].

Data analysis Qualitative data management and analysis will be conducted with MAXQDA software.

All interview recordings will be transcribed, translated, and uploaded to MAXQDA for coding and analysis. We will code all documents by document type (e.g., provider or PLWH interview), demographic information (city/region, years since HIV diagnosis, gender, socioeconomic status), role (director, frontline staff, policy maker). Then, we will create and apply text codes that reflect key dimensions of the DAP framework, including provider factors (prior experience with incorporating data in service provision, attitudes toward the D2C strategy, educational and training backgrounds); organizational factors (leadership buy-in, organizational climate, training and resource capacity); system factors (funding, contracts, policies); and client characteristics (comorbidities, prior experiences in care, level and type of need). In-depth interviews will be analyzed within the context of DAP to identify the system level, organizational, provider, and patient roles and characteristics that will inform the adaptation and implementation of the D2C strategy at each site and contextual factors that will need to be addressed for successful integration of a D2C strategy into the clinical setting. For example, data analysis may determine that HIV-positive PLWH need specific services that implementing organizations currently do not offer or that providers lack technical skills to retrieve and interpret acuity data. We will address these issues in the finalization of the D2C strategy, including identifying referral organizations, and through training, capacity-building, technical assistance strategies. We will also use findings from Aim 1 data analysis to match sites for paired randomization, as described below in Aim 2.

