D2C is a structural intervention designed to sustainably change the HIV care providers' practices and facilitate information exchange at the facility level. To address the implementation science questions by measuring the provider-level outcomes and avoid contamination of the control condition due to unblinded allocation of intervention at the patient level, we propose a cluster-randomized trial design for this pilot study and the prospective RCT. We will select eligible HIV clinics (see "Study Sites," above) and randomly assign them 1:1 either to the intervention or the control arms. To achieve greater comparability between the arms, we will match pairs of eligible sites based on organizational context factors derived from Aim 1 data analysis, including facility size and type (e.g., NGO vs. public clinic), service delivery structure (e.g., social workers vs. nurses), and existing services for HIV-positive PWID (e.g. Steps Toward Health) and will randomize within the pairs. This will minimize the degree of between-cluster variation within the groups and increase power and precision.

Randomization will be conducted by the data manager using a computer program.

Sample size

We used methodology from Hayes et al⁸⁴ to determine the effect size that the intervention needs to demonstrate in a feasible matched-pair randomized trial. We assumed the cluster size of 75 patients (based on the optimal case manager workload) with 5 clusters per arm (potentially manageable number given the existing research infrastructure in Ukraine), coefficient of variation between clusters within matched pairs equal to 0.15 (empirically estimated based on the data from 56 clinics in the ART OPTI study, see Previous Studies), power of 80% and 0.05 significance level. Proportion of participants re-engaging into ART within 3 months after inclusion into the study was used as the key outcome. Under the assumptions, the relative difference between the study arms should be at least 22% (e.g. 50% vs 72%). The adjacent chart shows the power and sample size of a pilot trial needed to detect this difference with 0.05 significance level. To achieve 80% power, we will need to recruit 160 participants, or 80 per arm. We propose to divide the sample equally between 4 sites (2 per arm) to test the matching procedures. We do not adjust for loss-to-follow-up because for our main outcomes (ART initiation, viral suppression), loss to follow-up is equal to not achieving the outcome.

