- use Acuity Tool to assess patient-identified financial, socioeconomic, and housing profiles and provide comprehensive internal or external referrals for supplemental or long-term resources;
- develop and implement personalized treatment plans for all clients based on the acuity assessments through existing case management programs;
- ensure accurate tracking and documentation of all interactions and activities with patients using the acuity tool and Tracking Module within the MIS;
- establish, develop, and maintain professional relationships with diverse treatment and service providers, including AIDS care, primary care, substance use, mental health, and social services;
- maintain current contact information using the Contact Information Form (Annex 0) and updates it at each visit.

Additionally, Case Managers assist Interviewers to schedule follow-up interviews (see below) in conjunction with the Intervention sessions (at 6 and 12 months).

Control Condition

Clinics randomized to the standard of care arm will continue to implement their client identification processes and case management as usual. One of the most common interventions with a focus on PWID is Steps Toward Health,⁸⁵ a case management program developed and tested through the PEPFAR-funded RESPOND project.^{8,86} It is theory-driven and standardized in manuals that contain background information, logic models, client assessment worksheets, step-by-step instructions for each session, and monitoring and evaluation guidelines. This 5-session intervention includes modules on self-care, HIV transmission risk reduction, drug treatment, and ART adherence. It does not include active outreach, client tracking, or tailored treatment components. Other possible interventions include Community-based Retention Intervention, Patients' School, and others.

Provision of these interventions (the fact of enrollment) will be recorded in the MIS by Recruiter, but the actual process data will not be collected.

Data Collection

Data on **primary outcomes** will be obtained from clinical records in the MIS and absence of data will be equal to not achieving the outcome, therefore the effective sample size will be exactly 160 patients. Data from the MIS will be extracted monthly (Annex 6). The primary outcomes are defined as:

- Engagement in HIV care: at least 3 clinical visits over at least 6 months within 12 months after study enrollment.

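### Clinics are paired only on organisational factors not shown to predict the outcome, although a past outcome rate for each clinic can be derived from the MIS before randomisation

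*Combined protocol and SAP*

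**What the plan says.** The Study Design section under Specific Aim 2 says "we will match pairs of eligible sites based on organizational context factors derived from Aim 1 data analysis". The factors it names are how large the facility is and of what kind, how its services are staffed, and what it already offers to HIV-positive people who inject drugs. The stated purpose is statistical: "This will minimize the degree of between-cluster variation within the groups and increase power and precision". The data analysis paragraph under Aim 1, which describes coding of in-depth interviews, confirms the source: "We will also use findings from Aim 1 data analysis to match sites for paired randomization". Neither section names a clinic's past outcome rate. The Statistical Analysis and Feasibility Assessment section adds pair indicators, site random intercepts and patient covariates, but no clinic-level past rate.

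On data availability, the Study Sites section makes it a selection criterion that the "MIS is fully operational and all patients are entered". The Background says "The MIS contains patient-level information on HIV care appointments kept, medication prescriptions, all diagnosed co-morbidities, and clinical and laboratory test results". Under Data Collection, primary outcome data "will be obtained from clinical records in the MIS".

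The Sample size section adds that the four sites serve to try out the matching procedure. It gives 0.15 as the coefficient of variation (CV) between clusters within matched pairs, estimated from 56 clinics in the ART OPTI study, which the Background describes as an evaluation based on MIS data.

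**The concern.** Pairing reduces the variance of the treatment contrast only to the extent that paired clinics would have had similar outcomes without the intervention. Size, type, staffing and existing services may predict return to ART or engagement, but the protocol offers no evidence that they do, and it states the gain in precision as a fact. A past rate of the same outcome is a natural candidate predictor. The team appears to have used MIS data to estimate between-clinic variation already.

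With one intervention clinic and one control clinic per pair, any prior gap between them enters the effect estimate directly. The feasibility rule is a 22-point difference in engagement. At a 50% rate and CV 0.15, the SD of one clinic's true rate is 0.15 × 50 = 7.5 points. The gap between two unrelated clinics then has SD 7.5 × √2 = 10.6 points, and its average over two pairs has SD 10.6/√2 = 7.5 points. That is large enough to matter to a 22-point rule.

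Also, without past rates beside trial rates, the pilot cannot show whether its matching reduced within-pair variation, which is part of its purpose.

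**Working it through.** **Inputs from the protocol.** Rates of 50% and 72% for ART re-engagement within 3 months; CV k = 0.15; four clinics in two pairs; 160/4 = 40 patients per clinic; significance level 0.05 (two-sided assumed). For the larger trial: 75 patients per cluster and 5 clusters per arm.

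**The plan's own figures.** Comparing two independent proportions with no clustering, 80 per arm gives 82.0% power by normal approximation and 81.6% by exact enumeration of the chi-square test (76 per arm would suffice). The 160 therefore takes no credit for matching and carries no penalty for clustering. The 5 clusters per arm reproduce as 4.78 rounded up, using the unmatched form of the cited method.

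**Standard error (SE) in the pilot when pairing is unrelated to outcome.** The variance of one pair difference is

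p0(1−p0)/m + p1(1−p1)/m + k²(p0² + p1²)
= 0.25/40 + 0.2016/40 + 0.0225 × (0.25 + 0.5184)
= 0.00625 + 0.00504 + 0.01729 = 0.02858.

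SE over two pairs = √(0.02858/2) = 0.1195, or 11.95 points.

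**Effect of pairing on a past rate.** Let r be the correlation between a clinic's past and trial-period rates (assumed; not in the documents). Simulating sets of four clinics, sorting them on the past rate and pairing neighbours gives the factor by which the within-pair variance shrinks. It multiplies only the 0.01729 term, so SE = √((0.01129 + 0.01729 × factor)/2).

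| r | Factor | SE (points) | Gain in information |
|---|---|---|---|
| 0.2 | 0.98 | 11.9 | about 1% |
| 0.3 | 0.95 | 11.8 | about 3% |
| 0.5 | 0.86 | 11.4 | about 9% |
| 0.7 | 0.73 | 10.9 | about 20% |
| 0.9 | 0.55 | 10.2 | about 37% |

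**How large r can be.** Past rates carry sampling error. With true between-clinic variance (0.15 × 0.5)² = 0.005625 and n past patients per clinic, reliability = 0.005625/(0.005625 + 0.25/n), and r cannot exceed its square root. For n = 40: 0.005625/0.011875 = 0.47, so r ≤ 0.69. For n = 150: 0.005625/0.007292 = 0.77, so r ≤ 0.88. Reaching r = 0.9 needs about 190 past patients per clinic and no drift over time. Study Sites requires only 150 registered patients with injecting drug use (IDU) as mode of transmission, and only some of them miss visits and return.

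**If organisational factors already help.** Suppose they alone achieve what r = 0.5 would, and the past rate achieves r = 0.7. The gain is (0.01129 + 0.01729 × 0.86)/(0.01129 + 0.01729 × 0.73) = 0.02616/0.02391 = 1.09, or about 10%. If both stand at 0.5, the gain is nil.

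**Effect on a formal test in the pilot.** A paired t test on two pairs (1 degree of freedom) has about 12% power at k = 0.15, and only 18% at k = 0.

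**The case against.** The case for leaving the matching as planned has real force.

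- **Population.** The MIS holds records, not a ready-made rate. Participants consent only after being reached, screened by phone and coming to the clinic (Patient outreach and First visit sections). A rate among everyone who missed a visit would mostly measure whether people come back at all. This stands, and it dictates how the rate must be defined. Missed-visit records are also known to need correction, which adds noise.
- **Baseline.** The protocol labels 0.15 as the CV within matched pairs, and the table treats it as the unmatched value. If organisational matching already achieves 0.15, the added gain could be smaller. This stands as a limit on the size.
- **Other aims.** Organisational matching also suits the provider-level and implementation outcomes, and the list of factors opens with a word that leaves it incomplete. Four clinics allow only three pairings, so a rule driven by the past rate could pair an NGO with a public clinic. This stands against giving the rate priority.
- **Consequence.** The 160 does not depend on matching, and no pairing rescues a two-pair significance test. This is true, but estimating the CV and trying out the matching are stated purposes of the pilot.

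A reader might infer that the past rate should override the other factors, that it would add 37% information, or that it is the only protection against clinic imbalance. The documents support none of these. The trade-off with three pairings is debatable, r = 0.9 is unlikely at clinics near the minimum size, and the analysis plan already includes pair effects and covariate adjustment, although two pairs leave little room for clinic-level adjustment.

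**Conclusion.** The point holds as a modest design improvement. The plan claims better precision from factors whose link to the outcome it does not show, and leaves unused a candidate matching factor that its own data system can supply before randomisation. Against pairing unrelated to outcome, the plausible gain runs from about 1% to about 20% in information (r from 0.2 to 0.7), with the SE falling from 11.95 points to no lower than about 10.9. This rests on an assumed correlation, on 0.15 as the unmatched CV, and on the 3-month ART rates of 50% and 72%. The feasibility rule concerns engagement in care, for which the documents give no separate CV. The gain is smaller, possibly nil, if the organisational factors already predict outcome.

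The firmer benefit is that past rates reported beside trial rates would let the pilot show whether matching reduced within-pair variation. Nothing here makes the 160 wrong.

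**What to change.** Before pairing, extract from the MIS for each selected clinic, over a recent past period, the rates of 12-month engagement (the feasibility outcome) and of 3-month ART (re-)initiation. Restrict the query to adults with documented IDU who missed a visit by more than 7 days and then returned, and count time from the return visit to mirror enrolment. The period must end early enough for 12 months of follow-up to be complete.

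In the Study Design section, add this rate to the matching factors alongside the organisational ones and state that it will be used to choose among pairings that are organisationally acceptable. In the analysis section, state that each clinic's past rate and its number of past patients will be reported beside its trial result, with the observed within-pair variation.

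The cost is one MIS query, a few sentences of text and possibly slightly looser organisational matching. It adds no patients. It has to be done before randomisation, because the pairing cannot be changed afterwards.

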We have powered this pilot study to evaluate feasibility of a prospective cluster RCT. The RCT will be considered feasible if the difference in the proportion of patients achieving the primary outcome (engagement in HIV care) will reach 22% between the study arms. We will estimate the impact of the intervention on the HIV care continuum using mixed effects models. For all outcomes, the data will have the same structure, with observations (t) nested within participants (i) nested within sites (j) nested within matched pairs (k). The correlations among observations will be addressed by using fixed-effects indicators for matched pair and normally distributed random intercepts for sites and for participants. Our mixed-effects models will include indicators for each of the two follow-up assessments, an indicator for site group assignment, and two group-assignment-by-follow-up interaction terms. We will also include sex/gender, age, and baseline covariates that have been identified in preliminary analyses as varying significantly across sites. A logit link function will be used for the primary outcome of ART (re-)initiation (defined above), and the coefficients for the two group-assignment-by-follow-up interaction terms will provide the estimates of the subject-specific intervention effects at 6 and 12 months post-baseline. We will examine the effects of sex/gender, age, substance use severity, ART history at baseline and other covariates in the multivariable models.

We will characterize patterns of behavior that impact HIV transmission (episodes of syringe sharing and episodes of unprotected intercourse in the prior 30 days without viral suppression) and we will use the same mixed-effects approach described above but with a log link function and negative

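### The 22-point difference given for 5 matched pairs of 75 has about 70% power, not 80%, if alpha is two-sided as the pilot sizing implies; it is also mislabelled as relative

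*Combined protocol and SAP*

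**What the plan says.** The Sample size section uses a cited cluster-trial method "to determine the effect size that the intervention needs to demonstrate in a feasible matched-pair randomized trial". Its inputs are:

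- "We assumed the cluster size of 75 patients" "with 5 clusters per arm";
- "coefficient of variation between clusters within matched pairs equal to 0.15";
- "power of 80% and 0.05 significance level".

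The outcome used for sizing is re-engagement into ART within 3 months. The result is: "Under the assumptions, the relative difference between the study arms should be at least 22% (e.g. 50% vs 72". The paragraph then sizes the pilot to detect the same difference at 0.05 significance and 80% power, and arrives at 160 participants, 80 per arm.

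Under Statistical Analysis and Feasibility Assessment, the full trial counts as feasible if the between-arm difference in engagement in HIV care "will reach 22% between the study arms". Neither section says whether alpha is one- or two-sided, and the formula is not printed.

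**The concern.** Five pairs leave only 4 degrees of freedom for a paired comparison, and the matched version of the cluster formula adds 2 clusters per arm where the unmatched version adds 1. With so few clusters, that extra unit decides whether 5 is enough. If 22 points is too small for the stated design, the plan understates the effect that the future trial needs in order to reach its stated power. The same number is the go/no-go threshold, so an observed 22-point difference would label as feasible a 5-pair trial whose type II error is 30 to 32% rather than 20%.

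The word *relative* adds a separate ambiguity, and the feasibility rule does not say which scale its 22% is on.

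**Working it through.** **Inputs.** From Sample size: m = 75 per cluster, c = 5 pairs, k = 0.15, p0 = 0.50, p1 = 0.72, alpha 0.05, power 80%. Assumed, because the text is silent: the standard form of the cited method (Hayes–Bennett), with k applied to each arm's own rate, and sidedness tried both ways.

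**Formula.** c = A + (zα + zβ)² × V / (p1 − p0)², where V = p0(1−p0)/m + p1(1−p1)/m + k²(p0² + p1²). A = 1 if unmatched, A = 2 if matched.

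V = 0.25/75 + 0.2016/75 + 0.0225 × (0.25 + 0.5184) = 0.00333 + 0.00269 + 0.01729 = 0.02331.

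- Two-sided: 7.849 × 0.02331 / 0.0484 = 3.78.
- One-sided: 6.183 × 0.02331 / 0.0484 = 2.98.

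**Reproducing the plan's figure (5 clusters per arm, 80% power, 22 points).**

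| Route | Clusters per arm | Power at 50% vs 72% | Points for 80% power |
|---|---|---|---|
| Matched, one-sided | 4.98 | 80.3% | 21.9 |
| Unmatched, two-sided, formula | 4.78 | 82.2% | 21.3 |
| Unmatched, two-sided, t with 8 df | – | 80.5% | 21.8 |
| Matched, two-sided, between-cluster SD fixed at k × p0 | 4.80 | 82.6% (79.6% by paired t) | 21.3 |
| **Matched, two-sided, as described** | **5.78** | **70.4%** | **25.1** |
| **Paired t with 4 df, two-sided** | – | **67.8%** | **26.3** |

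Steps for the last two rows:

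- Formula: √[(5 − 2) × 0.0484 / 0.02331] = 2.496, and 2.496 − 1.96 = 0.536, which gives 70.4%.
- Paired t: noncentrality 0.22 / √(0.02331/5) = 3.22 on 4 df gives 67.8%. A beta-binomial simulation of the paired t-test gave 67.5%.
- Six pairs: the formula gives √[4 × 0.0484 / 0.02331] − 1.96 = 0.922, or 82.2%; the paired t gives 80.3%. That is 6 × 2 × 75 = 900 patients rather than 750.

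**Which sidedness does the paragraph imply?** The pilot is a check, because it uses the same difference and significance level. For two proportions, n per arm = [zα√(2p̄(1−p̄)) + zβ√(p0(1−p0) + p1(1−p1))]² / (p1 − p0)², with p̄ = 0.61.

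- Two-sided: 76 per arm (85 with continuity correction); power at 80 per arm is 82.0%.
- One-sided: 60 per arm (69 with continuity correction); power at 80 per arm is 89.2%.

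The stated 80 per arm lies within the two-sided range and outside the one-sided range.

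**Dependence on the control rate.** Matched formula, two-sided, 5 pairs, 80% power: 18.8 points at 30% control, 22.1 at 40%, 25.1 at 50%, 28.1 at 60%.

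**Scale.** 72 − 50 = 22 points; 22/50 = 44% relative.

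**The case against.** The strongest reply is that the 22 can be reproduced for a matched trial. Sidedness is never stated, and one-sided 0.05 in the matched formula returns 4.98 pairs, 80.3% power and 21.9 points. A reader might infer that the sponsor ran an unmatched calculation by mistake. The documents do not show that: at least one matched route fits as well or better. What stands against the one-sided route is the pilot's 80 per arm, which would then use a different alpha under the same label. That evidence is indirect, since the power chart for the pilot is not shown. The fixed-SD route is also matched, but it replaces the stated input, a CV, with another quantity.

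Second, 50% is only an example rate. At 40% control, 22 points is right for the matched two-sided design. This stands, and it is why the corrected figure needs its baseline beside it.

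Third, a reader might infer that 25 or 26 should simply replace 22 in the feasibility rule. The documents do not support this. The figure was derived for ART re-engagement within 3 months; the rule concerns engagement in care, defined over 12 months under Data Collection, and no control rate or CV is given for that outcome.

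Fourth, taking *relative* literally gives 50% vs 61%, where 5 pairs would have about 26% power. The plan's own example rules out that reading, so the word is a slip in labelling and not a second design.

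Finally, the consequence is limited. The pilot is meant to estimate the effect size and CV, so the full trial would be re-sized. On the plan's CV, with 2 clusters of 40 per arm, the pilot difference has a standard error of √[(0.25/40 + 0.2016/40 + 0.01729)/2] = 0.12. A shift of 3 to 4 points is about a third of that. This lowers the practical stakes, but it does not make the stated power correct.

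**Conclusion.** The point holds in conditional form. With two-sided alpha 0.05, a CV of 0.15 applied in each arm, 5 matched pairs of 75 and the plan's own 50% vs 72%, power is about 68 to 70% rather than 80%. At 50% control, 80% power needs about 25 points (26 by paired t), or 6 pairs for 22 points. Two-sidedness is inferred from the pilot sizing and not stated.

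Of the calculations tried at 50% control, 22 is recovered only with one-sided alpha, which conflicts with the pilot sizing; with the matching penalty left out; or approximately with a constant between-cluster SD in place of the CV. Which of these was used cannot be told from the text.

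The label *relative* is wrong on any reading. Because the number also sets the feasibility threshold, the text should be corrected.

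**What to change.** In Sample size:

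- State the sidedness of alpha and the matched formula, and use the same alpha for the full-trial and pilot calculations.
- Describe the 22 as an absolute difference in percentage points.
- If alpha is two-sided, restate the result as about 68 to 70% power for 22 points with 5 pairs, or about 25 to 26 points for 80% power at a 50% control rate. Show how it varies with that rate. Six pairs at 22 points is the alternative.
- If one-sided alpha was intended, say so and reconcile it with the pilot's 160.
- If the detectable difference changes, say which difference the 160 is now sized for, since the two are linked in the text.

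In Statistical Analysis and Feasibility Assessment, express the threshold in absolute percentage points. Reconcile it with the restated figure and with the outcome it came from, rather than inserting 25 or 26 directly.

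The cost is text edits in two sections and no added pilot patients. The stated figure for the full trial becomes less favourable.
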